6.12.4 Global Evaluation of Product Effectiveness, Tolerability and Usability

At the end of the Treatment Phase (or withdrawal if earlier) subjects will be asked to provide their global evaluation of their allocated IP after using their allocated IP for 4-week. Subjects will be asked to rate their agreement using the following scale:

- Very Satisfied
- Somewhat Satisfied
- Neither Satisfied nor Dissatisfied

- Somewhat Dissatisfied
- Very Dissatisfied

6.12.5 Patients Global Impression of Change (PGIC)

At the end of the Treatment Phase (or withdrawal if earlier) subjects and male partners will be asked to complete a PGIC (Hugh H and Jennifer B, 2004). PGIC is a patient reported scale to assess patient perception of change in a condition or symptom following treatment. The subjects and male partners will be asked to rate the change in sexual intimacy experienced within their couple after using their allocated IP for 4-week. PGIC will be presented in a form of the visual analogue scale (VAS):

- -3 (Much Worse)
- -2
- -1
- 0 (No Change)
- 1
- 2
- 3 (Much Better)

6.13 Adverse Events

During scheduled visits, non-leading questions ('Are you experiencing any symptoms or complaints? / Have you felt unwell, suffered any complaints or taken any medication since... / Have you had any symptoms of complaints since the last time you were asked?') will be used to collect any AE/ADE experienced by the subject/male partner. Additionally, spontaneously reported AEs/ADEs will be collected. AE/ADE of male partners can be reported via a contact by the male partner with the clinical site or via the female subject at each visit or via the male partner at his visit.

The observation period for an individual subject/male partner will start after giving informed consent and will finish at the last visit of the Treatment Phase for the given individual subject/male partner. All AEs/ADEs that arise during the observation period will be recorded and an assessment of the AEs/ADEs will be performed as per [Section 8.1](#) by a medically qualified Investigator. If a subject/male partner has an AE/ADE that is still ongoing at the last visit, an attempt will be made by the Investigator to follow this up as per [Section 8.3](#).

If an untoward medical occurrence happens after the subject/male partner has signed the consent form but before administration of the device, it should be reported as an AE, including those associated with investigation procedures.

7 INVESTIGATION PROCEDURES BY VISIT

7.1 Investigation Flow Chart / Table of Investigation Procedures and Assessments

Table 7-1 Schedule of Assessments – Tolerance Phase

Procedure	Period	Screening	Tolerance Phase				Treatment Phase		
			Visit 1	7-Day Wash-Out Period	Visit 2 ¹		Visit 3 ²	Run-In Phase	Visit 2 ³
					Baseline	30 mins	2 hrs		
Informed consent (including male partners)		X							
Inclusion / Exclusion (including male partners)		X			X ⁵			X ⁵	X ⁵
Verbal Rating Scale (VRS) of Dyspareunia and Vaginal Dryness ⁶		X							
Demographics (including male partners)		X							
Medical history & prior therapies (including male partners)		X							
Concomitant medication (including male partners)		X	X	X	X	X	X	X	X
Physical examination		X		X ⁷			X ⁷		X ⁷
Pregnancy test		X					X ⁸		X ⁸
Lubricant Use History		X							

Procedure	Period	Screening	Tolerance Phase				Treatment Phase		
			Visit 1	7-Day Wash-Out Period	Visit 2 ¹		Visit 3 ²	Run-In Phase	Visit 2 ³
					Baseline	30 mins	2 hrs		
Randomisation ⁹		X							
Vaginal Epithelial Tolerability Assessment						X		X	X
Global Assessment of Vulvovaginal Tolerance									X
Overall Vulvovaginal Tolerance Rating Statement									X
Oral Examination/Assessment						X	X	X	X
Global Assessment of Oral Tolerance									X
Overall Oral Tolerance Rating Statement									X
SPQ – Tolerance Phase									X
[REDACTED]						■		■	■
[REDACTED]						■		■	
FSFI Questionnaire									X X
SPQ – Treatment Phase (including male partners)									X ¹¹ X

Procedure	Period	Screening	Tolerance Phase				Treatment Phase		
			Visit 1	7-Day Wash-Out Period	Visit 2 ¹		Visit 3 ²	Run-In Phase	Visit 2 ³
					Baseline	30 mins	2 hrs		
Global Evaluation of Product Effectiveness, Tolerability and Usability									X
Patients Global Impression of Change (PGIC) (including male partners)									X
Issue Subject Diary ¹²		X						X	X
Collect and Review Subject Diary									X X
IP Weighed ¹³									X X
IP Dispense									X
Collect Returned IP									X
Adverse Events (including male partners)		X	X	X	X	X	X	X	X

1. Tolerance Phase Visit 2 should be conducted within 10 days after Visit 1. Assessment window: 30 minutes \pm 15 minutes post application (oral mucosal tolerance only) and 2 hours \pm 15 minutes post application (VET, oral mucosal tolerance). [REDACTED]
2. Assessment window: 24 hours \pm 2 hours post application.
3. Visit 4 for subjects undergone the Tolerance Phase. Treatment Phase Visit 2 should be conducted within \pm 3 days after the completion of the 4-week Run-In Phase.
4. Visit 5 for subjects undergone the Tolerance Phase. Treatment Phase Visit 3 should be conducted within \pm 3 days after the completion of the 4-week IP use period.
5. Eligibility to be confirmed following screening assessments. Continued edibility will be confirmed at each clinical site visit.
6. Subjects having a score of 1 or 2 for vaginal dryness and 1 or 2 for dyspareunia on the VRS are to be considered for inclusion into the investigation.

Clinical Investigation Plan

Investigation No:
5025003

Protocol Version:
V3.0, 27-Oct-2022

Page 65 of 96

7. Physical examination, including gynaecological examination (Tolerance and Treatment phase) and oral examination (Tolerance Phase only), are to be performed if deemed necessary in the opinion of the Investigator.
8. Pregnancy test if deemed necessary by the Investigator.
9. Subjects will be randomised into the investigation upon completion of the screening activities and confirmation of subject's eligibility.
10. [REDACTED]
11. An SPQ is to be completed within 24 hours after first use of the allocated IP.
12. In the Treatment Phase, the diary will be issued at Visit 1 to capture subjects' compliance such as IP use, number of sexual acts etc during the run-in phase. A second diary will be issued at Visit 2 to capture their compliance over the 4-week IP use period.
13. In the Treatment Phase, IP will be weighed prior to being dispensed at Visit 2 and weighed upon being returned by subjects at Visit 3.

7.2 Visit 1 – Screening Visit

At the screening visit, subjects and male partners will be informed about the investigation as described in [Section 6.1](#) and [Section 6.2](#). They will be asked to provide written informed consent for their participation in the investigation, prior to performing any investigation specific assessments. Once informed consent has been obtained, the subjects will undergo clinical assessments consisting of:

- Demographics (including male partners)
- Medical history and prior therapies (including male partners)
- Physical examination, including gynaecological examination and oral examination
- The last menstrual period (the first date and the last date)
- Pregnancy test (for subjects of childbearing potential only)
- Concomitant medication and AEs (including male partners)
- Completion of VRS of dyspareunia and vaginal dryness
- Lubricant use history

Once screening activities have been completed and results are available confirming the subject's suitability to enter the investigation as per the inclusion/exclusion criteria, subjects and male partners will be reminded of the investigation's restrictions as per [Section 4.4](#). Subjects will be randomised into one of two treatment groups using [REDACTED]. Each group will include an approximate 1:1 ratio of pre-menopausal to post-menopausal females, with an allowed difference of up to 40:60 (up to a maximum of 60% in either sub-population).

A subset of 22 subjects will undergo the Tolerance Phase of the investigation prior to entering the Treatment Phase per the randomisation schedule. Subjects entering the Treatment Phase directly will be issued a diary and instructed to complete during the run-in phase.

All assessments conducted during the screening visit are detailed in [Section 6](#) and summarised in Table 7-1. All clinical assessments and test results will be entered into each subject's eCRF.

7.3 Tolerance Phase

7.3.1 Wash-Out Period

Subjects participating in the Tolerance Phase, will undergo a 7-day wash-out period. During this period, subjects are not permitted to use any personal lubricants or other remedies for vaginal dryness and will be asked to refrain from engaging in vaginal sex or any other vaginal penetrative sexual activity e.g. digital stimulation or use of sex toys. Subjects will also be prohibited from using any new oral products that are irregular to their normal dental hygiene routine or eating any new foods outside their normal diet.

7.3.2 Visit 2

Visit 2 should be conducted within 10 days after Visit 1. All requirements in the wash-out period must be followed until subjects attend the clinical site for Visit 2.

Following a 7-day wash-out period, subjects will return to the clinical site for the Tolerance Phase, where subjects' continued eligibility will be confirmed. Physical examination will be carried out if necessary, in the opinion of the investigator.

Once on the clinical site, subjects will be provided with a snack and drink, ahead of an oral water rinse. After the oral water rinse subjects will participate in an additional 30-minute oral wash out period during which they will be asked to refrain from using any oral products or consuming any foods/drinks. If necessary, subjects may have water, and this will be recorded.

The following baseline assessments and measurement will be performed prior to IP application:

- Vaginal Epithelial Tolerability (VET), performed by the gynaecologist
- Oral examination by the dermatologist after additional 30-minute wash-out
- [REDACTED]
- [REDACTED]
- [REDACTED]

For the vulvovaginal assessments, subjects will be trained by the site staff on how to apply the IP to the vagina and intimate area and will then make the single application of lubricant at the clinical site in preparation for the 2-hour post application vulvovaginal assessment. For the oral assessments, the clinical site staff will apply a pea-sized application of the IP and the respective comparator to the inner linings of the upper and lower lips of the subject on both sides of the mouth, according to the randomisation schedule. Subjects will be assessed at 30 minutes (± 15 minutes) post application (oral mucosal tolerance only) and 2 hours (± 15 minutes) post application (VET, oral mucosal tolerance, [REDACTED]). In the first 2 hours post application, subjects will be asked to refrain from consuming any foods/drinks. If necessary, subjects may have water, and this will be recorded.

Subject's last menstrual period (the first date and the last date) will be recorded if the data is different from Visit 1. AEs will be collected using a general non-leading question. In addition, spontaneously reported AEs will be collected. Concomitant medication changes will be recorded.

While subjects are at home, they will be instructed to abstain from any vaginal penetrative activity including sexual activity or insertion of tampons and will refrain from using any vaginal products such as moisturisers or intimate washes. They will also be instructed to eat and drink as normal however again will be prohibited from using any new oral products that are irregular to their normal dental hygiene routine or eating any new foods outside their normal diet. Subjects will not be provided with any product to take home as there will be no additional applications during the Tolerance Phase.

All assessments conducted during the Visit 2 are detailed in [Section 6](#) and summarised in Table 7-1. All clinical assessments and test results will be entered into each subject's eCRF.

7.3.3 Visit 3

Subjects will return to the clinical site for their 24-hour assessment. After confirmation of continued eligibility, subjects will undergo the following clinical assessments within the window of 24 hours ± 2 hours:

- Vaginal Epithelial Tolerability (VET), performed by the gynaecologist
- Oral Assessment by the dermatologist
- [REDACTED]
- [REDACTED]

Subjects will be asked to complete the SPQ – Tolerance Phase at the clinical site. At the end of the Tolerance Phase, the gynaecologist will complete a Global Assessment of Vulvovaginal/Oral Mucosal Tolerance for each subject and provide an Overall Vulvovaginal/Oral Mucosal Tolerance Rating Statement for each IP. The Investigator (in consultation with the gynaecologist and the dermatologist) will determine if the subject remains eligible to enter the Treatment Phase of the investigation, as per the inclusion/exclusion criteria and given that the subject has not experienced any untoward medical occurrence. Additionally, subjects will be issued a diary and instructed to complete during the run-in phase as they enter the Treatment Phase.

Subject's last menstrual period (the first date and the last date) will be recorded if the data is different from Visit 2. AEs will be collected using a general non-leading question. In addition, spontaneously reported AEs will be collected. Concomitant medication changes will be recorded.

All assessments conducted during the Visit 3 are detailed in [Section 6](#) and summarised in Table 7-1. All clinical assessments and test results will be entered into each subject's eCRF.

7.4 Treatment Phase

7.4.1 Run-In Phase

Following the confirmation of subject's eligibility, subjects entering the Treatment Phase will undergo a 4-week run-in phase. Those subjects that have completed the Tolerance Phase of the investigation, will move into the 4-week run-in phase of the Treatment Phase. During this run-in phase, subjects will be asked to refrain from using any personal lubricants or remedies for vaginal dryness during sexual activity. Subjects will be asked to consent to engaging in vaginal penetrative sex at least once per week during this 4-week period. The number of sexual intercourses may comprise twice in one week to account for a menstrual period break. Subjects will be asked to record into their diary the number and frequency of coital acts during this period, including when subjects were unable to have sexual intercourse without the use of a lubricant and/or for menstrual bleeding (pre-menopausal women).

7.4.2 Visit 2 – Baseline

This is Visit 4 for subjects undergone the Tolerance Phase. This visit should be conducted within ± 3 days after the completion of the 4-week Run-In Phase.

Subjects will return to the clinical site following the run-in phase, where the following will be performed:

- Assess subject's continued eligibility as per inclusion/exclusion criteria
- Physical examination, including gynaecological examination (if necessary, in the opinion of the Investigator)
- Completion of FSFI by the subject
- [REDACTED]
- [REDACTED]
- Collection of diary and review for compliance
- Issuing new diary for the IP use period & SPQ – Treatment Phase
- Weigh and dispense IP
- Recording of AEs and concomitant medication changes
- Recording subject's last menstrual period (the first date and the last date)

Upon completion of the FSFI, subjects will be trained on how to apply the IP to the vagina. Subject's allocated IP (as per the randomisation schedule) will be weighed prior to being dispensed for the subject to use at home for a 4-week IP use period. Subjects will be instructed to use their allocated IP when engaging in vaginal penetrative intercourse at least once a week. Regular lubricant users will be instructed to use the lubricant as they usually would i.e. for vaginal, anal and/or oral sexual intercourse, ensuring that the IP is used at least once a week for penile/vaginal intercourse. For safety purposes, those subjects who do not usually engage in anal or oral will be instructed to use the IP for penile/vaginal sexual intercourse only.

Subjects will also be issued a diary to record number of sex occasions, site of lubricant application and number of lubricant applications per sex occasion. Additionally, subjects will be instructed that the subject and the male partner should complete an SPQ – Treatment Phase after the first use of the IP at home, within 24 hours of the intercourse. Subjects will be reminded of the study restrictions as per [Section 4.4](#), after which subjects will be permitted to leave the clinical site.

All assessments conducted during Visit 2 are detailed in [Section 6](#) and summarised in Table 7-1. All clinical assessments and test results will be entered into each subject's eCRF.

7.4.3 Visit 3 (End of Investigation)

This is Visit 5 for subjects who have participated in the Tolerance Phase. This visit should be conducted within ± 3 days after the completion of the 4-week IP use period.

Subjects and male partners will return to the clinical site after the 4-week IP use period, where the following assessments will be performed:

- Completion of FSFI by the subject
- Completion of an SPQ – Treatment Phase by the subject and the male partner
- Completion of Global Evaluation of Product Effectiveness, Tolerability and Usability by the subject
- Completion of PGIC by the subject and the male partner

- Physical examination, including gynaecological examination (if necessary, in the opinion of the Investigator)
- Collection of diary and review for compliance
- Collect and weigh returned IP
- [REDACTED]
- [REDACTED]
- Recording of AEs and concomitant medication changes (including the male partner)
- Recording subject's last menstrual period (the first date and the last date)

All assessments conducted during the Visit 3 are detailed in [Section 6](#) and summarised in Table 7-1. All clinical assessments and test results will be entered into each subject's eCRF.

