6.12 Treatment Phase Variables

6.12.1 Female Sexual Function Index (FSFI)

The FSFI is a 19-item self-report questionnaire (paper) to measure sexual functioning in women. The questionnaire assesses six domains of sexual function (sexual desire, sexual arousal, lubrication, orgasm, satisfaction and pain) as well as a total score. The questionnaire requires a 4-week recall.

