9.3 Analysis Datasets

The Full Analysis Set (FAS) will include all randomised subjects who enter the Treatment Phase of the study. The FAS will be used to assess the primary endpoint and all other endpoints that are assessed during the Treatment Phase, with the exception of adverse events. Subjects will be assigned to treatment to which they were randomised.

For the FSFI (total score and percentage of subjects achieving at least a 4-point change in total score), an analysis will also be performed on the Per Protocol (PP) population. The PP population will exclude subjects who have not been compliant with the requirements of at least one coital act per week during both the run-in and 4-week IP use period of the Treatment Phase, as well as using IP at least once per week for penile/vaginal intercourse during the treatment period. In addition, subjects who use less than 80% of their assigned product (<9.6g) will be removed from the PP population. Subjects may be excluded from the PP population due to other reasons that may impact the evaluation of study products and these will be identified prior to database lock. Subjects will be assigned to treatment received.

The Safety Population will include all randomised subjects and will include subjects who take part in the Tolerance Phase and/or the Treatment Phase. The Safety Population will be used for producing demographic, adverse event and other safety tables. Subjects will be assigned to treatment received.

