16 APPENDICES

16.1 Appendix 1: Female Sexual Function Index (FSFI)®

FEMALE SEXUAL FUNCTION INDEX (FSFI)®

INSTRUCTIONS: These questions are about your sexual feelings and responses during the past 4 weeks. Please answer the following questions as honestly and clearly as possible. Your responses will be kept completely confidential. In answering these questions, the following definitions apply:

Sexual activity can include caressing, foreplay, masturbation and vaginal intercourse.

Sexual intercourse is defined as penile penetration (entry) of the vagina.

Sexual stimulation includes situations like foreplay with a partner, self-stimulation (masturbation) or sexual fantasy.

TICK ONLY ONE BOX PER QUESTION

Sexual desire or interest is a feeling that includes wanting to have a sexual experience, feeling receptive to a partner's sexual initiation and thinking or fantasising about having sex.

1. Over the past 4 weeks, how often have you felt sexual desire or interest?

- 5 = Almost always or always
- 4 = Most of the time (more than half the time)
- 3 = Some of the time (about half the time)
- 2 = Occasionally (less than half the time)
- 1 = Almost never or never

2. Over the past 4 weeks, how would you rate your level (degree) of sexual desire or interest?

- 5 = Very high
- 4 = High
- 3 = Moderate
- 2 = Low
- 1 = Very low or none at all

Copyright ©2000 All Rights Reserved

FSFI - UK English - Final version - 17 Jan 07 - Mapi Research Institute.
ID296

Sexual arousal is a feeling that includes both the physical and mental aspects of sexual excitement. It may include feelings of warmth or tingling in the genitals, lubrication (wetness), or muscle contractions.

3. Over the past 4 weeks, how often have you felt sexually aroused ("turned on") during sexual activity or intercourse?

0 = No sexual activity
5 = Almost always or always
4 = Most of the time (more than half the time)
3 = Some of the time (about half the time)
2 = Occasionally (less than half the time)
1 = Almost never or never

4. Over the past 4 weeks, how would you rate your level of sexual arousal ("being turned on") during sexual activity or intercourse?

0 = No sexual activity
5 = Very high
4 = High
3 = Moderate
2 = Low
1 = Very low or none at all

5. Over the past 4 weeks, how confident have you felt about becoming sexually aroused during sexual activity or intercourse?

0 = No sexual activity
5 = Very highly confident
4 = Highly confident
3 = Moderately confident
2 = Slightly confident

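### The ± 3 day window lets the 4-week FSFI be completed early, so an early Visit 3 recalls up to 3 lubricant-free run-in days

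*Combined protocol and SAP*

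**What the plan says.** Section 7.4.3 sets the timing of the 4-week visit: "This visit should be conducted within ± 3 days after the completion of the 4-week IP use period". Section 7.4.2 does the same for baseline: "This visit should be conducted within ± 3 days after the completion of the 4-week Run-In Phase". Table 7-1 footnotes 3 and 4 repeat both windows. Yet 7.4.3 also describes couples as coming back after the use period, 7.4.2 describes women as coming back following the run-in, and 9.5.1.1 defines the two scores as those at the end of each period.

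On the instrument, section 6.12.1 states: "The questionnaire requires a 4-week recall". The form in Appendix 1 opens: "These questions are about your sexual feelings and responses during the past 4 weeks".

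The two periods differ in the one thing under study. In the run-in, per 7.4.1, "subjects will be asked to refrain from using any personal lubricants or remedies for vaginal dryness during sexual activity", while women are asked to consent to "engaging in vaginal penetrative sex at least once per week during this 4-week period". At Visit 2, after the baseline FSFI, the product is "dispensed for the subject to use at home for a 4-week IP use period".

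The primary endpoint (9.5.1.1) is the Visit 3 total FSFI minus the baseline total. Section 2.2 asks for a statistically significant and clinically important change, with +4 points as the minimum important difference. Section 9.5.2.1 counts women who gain at least 4 points. Section 9.8 analyses data as collected. Neither 9.8 nor the named per-protocol exclusions in 9.3 has a rule for an FSFI completed early.

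**The concern.** The run-in and the use period are each as long as the questionnaire's recall. Each score therefore describes only its own period if the visit falls on or after the last day of that period, and the minus side of the window removes this guarantee. At a Visit 3 held on day 25, the woman is asked about 25 days with the product available and 3 days of run-in without lubricant. If the product helps, those 3 days pull her Visit 3 score toward her baseline. Her change is then understated because of her appointment date.

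At stake is the reading of the result against 4 points, both for the success criterion and for each woman's responder status. The baseline has a related problem: an early Visit 2 recalls days before the run-in began.

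**Working it through.** **Inputs.** Recall is 4 weeks, taken as 28 days (6.12.1, Appendix 1). The window is −3 to +3 days (7.4.2, 7.4.3, Table 7-1 footnotes 3 and 4). The threshold is +4 points (2.2). The use period is taken to start at dispensing in Visit 2, as 7.4.2 implies; the plan does not define the start formally.

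**Share of recall in the run-in.** For a Visit 3 held d days early, share = d/28. This step needs no model of scoring.

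**Effect on the change.** Assumption: every recalled day counts equally. Then measured change = true change × (28 − d)/28.

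| Days early | Share in run-in | True +4 reads |
|---|---|---|
| 1 | 1/28 = 3.6% | 4 × 27/28 = 3.86 |
| 2 | 2/28 = 7.1% | 4 × 26/28 = 3.71 |
| 3 | 3/28 = 10.7% | 4 × 25/28 = 3.57 |

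To show +4 at 3 days early, the true gain would have to be 4 × 28/25 = 4.48.

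**Average.** Assumption: visits spread evenly over the seven allowed days. Mean days early = (3 + 2 + 1 + 0 + 0 + 0 + 0)/7 = 0.857. Share = 0.857/28 = 3.06%. Loss = 4 × 0.0306 = 0.12 points.

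**Other weighting.** If weight follows sex acts instead of days, a woman with no act on the carried-over days loses nothing. One run-in act beside four acts with the product costs 1/5 = 20%, so +4 reads 3.20. At one act per week, the chance that a given 3-day stretch holds one is roughly 3/7. The equal-day figures are illustrations, not predictions.

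**Power.** Section 3.3 gives 24 completers per group for 90% power. The visible text shows no standard deviation, so this cannot be reproduced independently. Solving a paired t-test (two-sided alpha 0.025, difference 4, n = 24) for 90% power gives an SD of 5.25. Using that SD:

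| Visit 3 timing | n = 24 | n = 30 |
|---|---|---|
| None early | 90.0% | 95.9% |
| Evenly spread | 88.0% | 94.8% |
| All 3 days early | 81.7% | 90.6% |

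**Baseline.** A Visit 2 held 3 days early recalls 3 days before the run-in. For the Tolerance subset, those days fall in or next to a phase with a ban on vaginal penetrative sex (Table 4-1) and one product application (7.3.2). For direct entrants they precede screening, when the Table 4-1 restrictions begin. The documents give no basis for a direction or a size.

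**After the change.** With no Visit 3 before day 28, 0 of 28 recalled days fall in the run-in, and a true +4 stays 4.00 on the same model.

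**The case against.** The strongest reply is that visits after completion are plainly meant. Sections 7.4.2, 7.4.3 and 9.5.1.1 all speak of the end of the period or later, and a two-sided tolerance after a completion is awkward wording. That stands as a reading of intent, but the site works to the window, and the window admits day 25. If only later visits were meant, the same edit corrects the wording.

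A second reply is that the effect is small and depends on the model. This stands. FSFI items are ordinal categories, and a 3-day shift need not move an answer. Most arousal, lubrication, orgasm and pain items concern sexual activity, stimulation or penetration, so days without sex add little. Women do not recall to the exact day, and the documents do not say how many visits would be early. The formal test is against no change, so the error is on the cautious side.

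Two stronger readings are tempting.

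- **Per-protocol exclusion.** A reader might infer that compliant women seen early would be lost through the amount rule in 9.3, under which "subjects who use less than 80% of their assigned product (<9.6g) will be removed from the PP population". The documents do not support this. A woman who has used the product in only three weeks already fails the separate weekly-use rule in 9.3. One who has used 3 g in each of four weeks has used 4 × 3 = 12 g, of which 9.6 g is 80%. The per-protocol analysis is also secondary; the primary analysis uses the full analysis set.
- **Compounding by an early baseline.** A reader might infer that earlier lubricant use raises an early baseline and shrinks the change further. Universal exclusion 21 in 4.3.1 excludes women unwilling to stop over-the-counter vulvovaginal products at least 7 days before screening, which on a natural reading covers the 3 days at issue. In the Tolerance subset, the ban on intercourse adds no penetrative act to the recall.

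**Conclusion.** The point holds as a mismatch between visit window and recall period, and as a conflict within 7.4.3. A woman seen 1 to 3 days early at Visit 3 has 3.6% to 10.7% of her recall in the lubricant-free run-in. If days count equally and the product works, her true +4 reads 3.86 to 3.57. The average loss is about 0.12 points if visits spread evenly. These sizes also assume that the use period starts at dispensing.

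The consequence is limited to early attenders and works against the product, so it does not threaten the test against zero. It matters mainly where 4 points is the line: the success criterion and the responder count. It would be too strong to say that the window as such shrinks the primary result, because late and on-time visits carry no run-in days and the share of early visits is unknown. The baseline part is real but cannot be sized. This is a cheap improvement, not a flaw that undermines the trial.

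**What to change.** Change ± 3 days to 0 to +3 days for both FSFI visits, in sections 7.4.2 and 7.4.3 and in Table 7-1 footnotes 3 and 4. This goes no later than the latest day already allowed, keeps run-in days out of the Visit 3 recall and pre-run-in days out of the baseline recall, and removes the conflict with the wording on returning after the use period.

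The sponsor should also reconcile the window with two other parts of the plan:

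- **The stated 4-week use period.** The plan should say when it starts and what applies on any days between its end and a later visit. The present window already raises that question.
- **The per-protocol weekly-use and 9.6 g rules in 9.3.** They do not say how a use period shorter or longer than four weeks is counted.

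The cost is the wording of two sections and two footnotes. The downside is that the site can no longer book early appointments.
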